#### Analysis sets

#### **Full Analysis Set**

The Full Analysis Set (FAS) comprises all subjects to whom study treatment has been assigned by randomization. According to the intent to treat principle, subjects will be analyzed according to the treatment they have been assigned to during the randomization procedure.

#### **Safety Set**

The Safety Set includes all subjects who received at least one administration of study treatment. Subjects will be analyzed according to the study treatment received, where treatment received is defined as the randomized treatment if the subject took that treatment (at least one administration or phlebotomy) or the first treatment received if the randomized treatment was never received.

#### Screen Failures

Screen failures are subjects who have signed the informed consent and who failed to be randomized for any reason (i.e. failing to meet inclusion or exclusion criteria or any other screening procedure).

#### Withdrawal of Informed Consent

Any data collected in the clinical database after a subject withdraws informed consent from all further participation in the trial, will not be included in the analysis. The date on which a subject withdraws full consent is recorded in the eCRF.

Death events may be used in the analysis if captured from public records (registers), local law and subject informed consent permitting.

# 2.1.2 Subgroup of Interest

NA

# 2.2 Disposition, Demographics and Other Baseline Characteristics

The FAS will be used for all baseline and demographic summaries and listings, unless otherwise specified. Summaries will be reported by treatment arm and for all subjects and listings will be reported by treatment arm to assess baseline comparability. No inferential statistics will be provided.

# 2.2.1 Subject Disposition

Enrollment by country and center will be summarized by treatment arm using the FAS. The number (%) of randomized subjects included in the FAS will be presented overall and by treatment group. The total number of screen failures will also be displayed in listings. The number (%) of subjects in the FAS who discontinued the study phases and the reason for discontinuation will be presented overall and by treatment group.

The following summaries will be provided (with % based on the total number of FAS subjects):

- Number (%) of subjects who were randomized (based on data from IRT system)
- Number (%) of subjects who were randomized but not treated (based on 'ZQ' & "FAZU" eCRF page)
- Number (%) of subjects who were treated (based on 'ZQ' & "FAZU" eCRF pages of each study treatment component completed with non-zero dose administered)
- Number (%) of subjects who discontinued the study treatment phase (based on the 'End of Treatment Phase' page)
- Primary reason for study treatment phase discontinuation (based on the 'End of Treatment Phase' page)
- Number (%) of subjects who have entered the post-treatment follow-up (based on the 'End of Treatment Phase' page)
- Number (%) of subjects who have discontinued from the post-treatment follow-up (based on the End of Post-treatment follow-up page)
- Reasons for discontinuation from the post-treatment follow-up (based on End of Post-treatment follow-up page)

Listings will also be generated for the subject disposition.

#### **Protocol Deviations**

The number (%) of subjects in the FAS with any protocol deviation will be tabulated by deviation category (as specified in the study Data Handling Plan) overall and by treatment group for the FAS.

All protocol deviations will be listed based on FAS. Subjects with COVID-19 related protocol deviations will be presented separately in the table and listing for FAS by category and relationship.

Novartis	Confidential	Page 16 of 36
SAP Amendment 1		Study No. CICL670F2203

The full list of protocol deviations is documented in the Study Specification Document (SSD). The COVID-related protocol deviations and relationship to pandemic will be identified and maintained in an independent tracker located in the document management system in the "CREDI Studies/ICL670F2203/TMF (Study Level)/Protocol Deviations" folder. The latest available tracker prior to database lock will be used.

#### Analysis Sets

The number (%) of subjects in each analysis set (defined in Section 2.1.1) will be summarized by treatment group.

#### 2.2.2 Demographics and Other Baseline Characteristics

The FAS will be used for all subject demographic and baseline characteristic summaries and listings, unless otherwise specified.

#### **Basic Demographic Data**

All demographic and baseline disease characteristics data will be summarized and listed by treatment arm. Categorical data (e.g. gender, age groups: 18 to <65 and  $\geq$ 65 years, race, and ethnicity) will be summarized by frequency counts and percentages; the number and percentage of subjects with missing data will be provided. Continuous data (e.g. age and weight) will be summarized by descriptive statistics (N, mean, median, standard deviation, minimum and maximum).

The number of subjects by sex and age categories and the number of subjects by race will be tabulated.

#### **Phlebotomy History**

Summary statistics will be provided for the volume of blood removed (average of the volume removed per subject) and the frequency (number of procedures per subject) of phlebotomy procedure (based on records reported before the randomization date in 'Phlebotomy Record' page).

Average Volume Removed per subject = Sum of Volume removed/frequency A listing will also be provided.

# **Medical History**

Medical history and ongoing conditions entered on (e) CRF will be summarized and listed by treatment arm. Separate summaries will be presented for ongoing and historical medical conditions. The summaries will be presented by primary system organ class (SOC), preferred term (PT) and treatment arm. Medical history and current medical conditions will be coded using the Medical Dictionary for Regulatory Activities (MedDRA) terminology. The MedDRA version used for reporting will be specified in the CSR and as a footnote in the applicable tables/listings.

Ocular medical history and ongoing conditions will be summarized and listed by treatment arm.

#### **Other Baseline Characteristics**

Descriptive statistics, frequency counts and percentages will be tabulated by treatment arm, as appropriate for history of cirrhosis (yes or no), clinically significant abnormality in ECG (yes or no) and overall interpretation in audiometric test (normal or clinically significant or insignificant abnormality) on the Safety set.

The Serum Ferritin at baseline will be summarized as both continuous (descriptive statistics) and categorical variable. It will be categorized as:  $<1000, \ge 1000$  to  $2000, >2000 \ \mu g/L$ 

All data collected will be listed.

# 2.3 Treatments (Study Treatment, Rescue Medication, Concomitant Therapies, Compliance)

The Safety Set will be used for medication data summaries and listings, unless otherwise specified.

#### 2.3.1 Study Treatment / Compliance

#### **Deferasirox FCT**

Duration of exposure, daily dose, cumulative dose, dose intensity (DI) and relative dose intensity (RDI) will be summarized by treatment arm. Duration of exposure will be categorized into time intervals; frequency counts and percentages will be presented for the number (%) of subjects in each interval. The number (%) of subjects who have dose reductions, increases, or interruptions, and the reasons, will be summarized by treatment group.

Subject level listings of all doses administered on treatment along with dose change reasons will be produced.

The safety set will be used for all summaries and listings of study treatment.

#### 1. Duration of Exposure & Daily Dose

• **Duration of exposure to DFX FCT (days)** = (date of last administration of study treatment) – (date of first administration of study treatment) + 1.

Summary of duration of exposure of DFX FCT in appropriate time units will include categorical summaries based on <12, 12-<24, 24-<52, 52-<76 and >76 weeks and continuous summaries (i.e. mean, standard deviation etc.).

- Average Actual Daily Dose (mg/kg/day) = Sum of all ((Dose X/current weight) \* Corresponding duration of exposure on dose X) / overall duration of exposure
- Average Planned Daily Dose (mg/kg/day) = Sum of all (Dose X \* Corresponding duration of exposure on dose X) / overall duration of exposure

Average daily dose is the dose over all days between first and last dose, excluding interruptions. The actual dose in mg/kg/day will be obtained by dividing the actual total daily dose administered in the DAR eCRF page by the last available weight at the time of

Novartis	
SAP Amendment 1	

dose administration reported in the vital signs eCRF page. The planned dose in the eCRF is reported in mg/Kg unit, and therefore the dose is already adjusted for the subject weight when calculating the average planned daily dose.

#### 2. Cumulative Dose

The planned daily dose of a subject is collected on the CRF page as dose prescribed in mg/kg/day and the actual daily dose is calculated by dividing the total daily dose collected on the CRF page in mg by the current weight (kg) corresponding to that visit. The current weight is equal to the weight on the same visit when dose had been administered or the last available weight before the dosing visit if the same visit weight is missing. Cumulative dose (mg/kg) is defined as the sum over the daily doses of all days between first and last dose.

Cumulative dose = sum of (daily dose at a visit \* (end date of dose - start date of dose +1).

- The **planned cumulative dose (mg/kg)** for DFX FCT refers to the total planned dose as per the protocol up to the last administration of study treatment.
- The **actual cumulative dose (mg/kg)** refers to the total actual dose administered, over the duration for which the subject is on the DFX FCT as documented in the Dose Administration eCRF.

For subjects who did not take any drug the cumulative dose is by definition equal to zero.

The actual cumulative dose is the sum of the non-zero doses recorded over the dosing period and the planned cumulative dose is the planned starting dose summed over the same dosing period.

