10.3 Treatments (study treatment, concomitant therapies, compliance)

The Safety set will be used for the analyses below. Categorical data will be summarized as frequencies and percentages. For continuous data, mean, standard deviation, median, 25th and 75th percentiles, minimum, and maximum will be presented, as appropriate.

For deferasirox, the duration of exposure in months and in categories (<3 months, 3-<6 months, 6-<12 months, 12-<18 months and >18 months); as well as average planned dose, actual daily doses (mg/kg/day) and percentage of planned dose taken (ratio of cumulative actual on cumulative planned dose) will be summarized using descriptive statistics. The number of patients with dose adjustments (reductions, interruption, or permanent discontinuation) and the reasons will be summarized by treatment group; all dosing data will be listed.

For phlebotomy, summary statistics will be provided for the volume of blood removed and the frequency.

Concomitant medications and significant non-drug therapies prior to and after the start of the study treatment will be listed and summarized by treatment group, according to the Anatomical Therapeutic Chemical classification system.

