# 3. Dose Intensity and Relative Dose Intensity

• Actual Dose Intensity (DI) for subjects with non-zero duration of exposure is defined as follows:

DI (mg/kg/day) = Actual Cumulative dose (mg/kg) / Duration of exposure to DFX FCT (day).

For subjects who did not take any drug the DI is by definition equal to zero. The denominator for DI, i.e., duration of exposure includes days of 0 doses.

• Planned Dose Intensity (PDI) is defined as follows:

PDI (mg/kg/day) = Planned Cumulative dose (mg/kg) / Duration of exposure to DFX FCT (day).

• Relative Dose Intensity (RDI) is defined as follows:

RDI = [DI (mg/kg/day) / PDI (mg/kg/day)]\*100.

The actual dose intensity and relative dose intensity will be summarized using descriptive statistics using the Safety Set. Additionally, categories of the RDI ( $\leq 75\%$ , >75% -90%, >90%-110%, >110%) will be summarized through frequency and percentage.

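### SAP 2.3.1 contradicts itself on planned cumulative dose; under its starting-dose sentence, relative dose intensity mixes adherence with protocol-directed dosing

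*SAP*

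**What the plan says.** SAP 2.3.1, under Cumulative Dose, makes three statements about the planned dose.

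- It opens: "The planned daily dose of a subject is collected on the CRF page as dose prescribed in mg/kg/day". The general formula that follows multiplies the daily dose at a visit by the days on that dose and sums. Together these give a denominator that follows the prescription.
- A bullet says that the planned cumulative dose "refers to the total planned dose as per the protocol up to the last administration of study treatment", without saying whether that includes ferritin-based dose changes.
- The paragraph closes: "the planned cumulative dose is the planned starting dose summed over the same dosing period".

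The next item of SAP 2.3.1 carries the quantity forward: "PDI (mg/kg/day) = Planned Cumulative dose (mg/kg) / Duration of exposure to DFX FCT (day"), with RDI equal to 100 times actual over planned dose intensity. RDI is summarized and tabulated in four classes: 75% or less, above 75 to 90%, above 90 to 110%, and above 110%. On zero-dose days it says: "The denominator for DI, i.e., duration of exposure includes days of 0 doses".

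Protocol 10.3 asks for the "percentage of planned dose taken (ratio of cumulative actual on cumulative planned dose"). SAP Section 4, which lists changes from the protocol's analyses, does not mention a starting-dose denominator.

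**The concern.** In a fixed-dose trial the starting dose and the prescribed dose are the same, and the closing sentence would do no harm. Here the dose can move. Protocol 6.1.1 and Table 6-2 start everyone at 7 mg/kg/day. After 12 weeks they allow 3.5, 7, 10.5 or 14 mg/kg/day according to serum ferritin. They require interruption at 100 µg/L or below, which is also the primary response criterion, and they allow a restart at 3.5 mg/kg/day.

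Measured against a constant 7 mg/kg/day, an adherent patient who is stepped down, stepped up, or held and restarted gets an RDI that mixes adherence with what the protocol directed. A reader of the RDI table could not tell a patient who missed tablets from one who was stepped down. The result would also not be the percentage of planned dose that Protocol 10.3 asks for.

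**Working it through.** The documents give no numerical RDI, so there is no figure to reproduce. The check applies the SAP's formulas to dose courses built from the protocol's own steps. The ferritin courses behind them are assumptions.

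**Formula.** Actual and planned dose intensity are both divided by the same duration of exposure, so duration cancels:

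RDI = 100 × actual cumulative dose / planned cumulative dose.

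The choice of planned cumulative dose therefore decides the result.

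**Inputs.** Starting dose 7 mg/kg/day; first ferritin-based change at 12 weeks; steps of at most 3.5 mg/kg/day per month; restart at 3.5 mg/kg/day (Protocol 6.1.1); 104 weeks of treatment (Protocol 7.1.4). Every patient takes every prescribed dose. Tablet rounding is ignored at first. Cumulative doses are in mg/kg/day × weeks; the factor of 7 days per week cancels.

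| Course | Actual | Starting dose × weeks | RDI, starting dose | RDI, prescribed dose |
|---|---|---|---|---|
| 12 wk at 7, 40 wk at 3.5 | 84 + 140 = 224 | 7 × 52 = 364 | 61.5% | 100% |
| 12 wk at 7, 28 wk at 3.5, 30-wk hold, 34 wk at 3.5; hold counted | 84 + 98 + 119 = 301 | 7 × 104 = 728 | 41.3% | 100%, hold planned as 0 |
| Same course; hold not counted | 301 | 7 × 74 = 518 | 58.1% | 100% |
| 12 wk at 7, 4 wk at 10.5, 88 wk at 14 | 84 + 42 + 1232 = 1358 | 7 × 104 = 728 | 186.5% | 100% |

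The two hold rows are needed because the closing sentence does not say whether interruption days belong to the dosing period. The sentence on zero-dose days concerns the duration of exposure, which points towards counting them.

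**How little change is needed.** After 84 days at 7 (588 mg/kg), with d further days:

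- At 3.5 mg/kg/day, RDI = (588 + 3.5d)/(588 + 7d). At d = 21 this is 661.5/735 = 90%; at d = 84 it is 882/1176 = 75%.
- At 10.5 mg/kg/day, RDI = (588 + 10.5d)/(588 + 7d). It equals 110% when 2.8d = 58.8, so it passes 110% after 21 days.

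**Conflict with another output.** The same SAP section builds the average planned daily dose from the planned mg/kg dose on the eCRF, excluding interruptions. For the first course, which has none, that average is 224/52 = 4.31 mg/kg/day, while planned dose intensity under the closing sentence is 7.0. One report would give two planned doses for one patient over the same days.

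**Tablet rounding.** The SAP computes actual dose as mg divided by weight. From the tables in Protocol Appendix 14.1, the ratio of dispensed to prescribed dose for an adherent patient is:

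- at 7 mg/kg/day, 270/(45 × 7) = 85.7% at 45 kg and 360/(46 × 7) = 111.8% at 46 kg;
- at 3.5 mg/kg/day, 180/(64 × 3.5) = 80.4% at 64 kg and 270/(65 × 3.5) = 118.7% at 65 kg.

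The prescribed-dose RDI is therefore 100% only before rounding.

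**The case against.** The best reply is that the SAP already holds the right definition. Its opening sentence and formula give the prescribed-dose denominator, and only one sentence departs from it. That is fair: the fault is a contradiction to be reconciled, and the documents do not settle which version would be programmed. The closing sentence is the most explicit of the three, though, so the risk is real.

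A second reply is that intensity relative to the starting dose is a legitimate measure, and that the SAP never calls RDI adherence. The first part stands if the ratio is labelled as such. But RDI has the form of the protocol's percentage of planned dose taken and sits in a section headed Study Treatment / Compliance, so it will be read that way.

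Third, other outputs carry part of the information: average actual and planned daily doses; dose reductions, increases and interruptions with reasons; and a listing of all doses. This limits the harm. It does not correct the RDI classes.

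A reader might go further and infer that good responders will generally fall in the lowest RDI class and high-ferritin patients in the highest. The documents do not support that. Ferritin-based adjustment is as needed; only the interruption at target is mandatory. Exposure ends at the last non-zero dose, so a hold without a restart never enters the calculation. Even with the starting dose as denominator:

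- a responder dosed only at 7 mg/kg/day and not restarted has an RDI of 100%;
- 12 weeks at 7 and 11 at 3.5 without a restart gives (84 + 38.5)/161 = 76.1%, above the lowest class;
- 12 weeks at 7, 12 at 10.5 and 80 at 7 gives (84 + 126 + 560)/728 = 105.8%, inside the class from above 90 to 110%.

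**Conclusion.** The contradiction is real and should be resolved before RDI is programmed. Under the closing sentence, adherent patients whose dose leaves 7 mg/kg/day, or who restart after the hold at target, get an RDI that does not give Protocol 10.3's percentage of planned dose taken. The illustrative courses run from 41% (58% if hold days are left out) to 187%, where the prescribed-dose denominator gives 100% before rounding.

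The size rests on assumed ferritin courses. The documents give no distribution from which to say how many patients would be affected. Patients kept at 7 mg/kg/day throughout, or held without a restart after dosing only at 7, are not affected. RDI is a descriptive exposure summary: no primary, key secondary or ocular endpoint depends on it, and the planned efficacy and ocular analyses involve no hypothesis test. This is a correction that should be made, not a threat to the trial's main results.

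**What to change.** In SAP 2.3.1, replace the closing sentence of the cumulative-dose paragraph. Define planned cumulative dose as the sum, over dosing records, of the prescribed mg/kg/day times the days on that record, and use it in both planned dose intensity and RDI.

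State how interruption days count:

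- Days interrupted because ferritin reached 100 µg/L or below, identified from the recorded interruption reason, count as zero planned dose.
- During interruptions for toxicity or any other reason, the prescribed dose stays as planned. Setting every interruption to zero would hide dose loss from toxicity.

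If a ratio to the starting dose is also wanted, report it under a separate label. Add a table footnote that tablet rounding alone can move adherent patients outside the class from above 90 to 110%.

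The cost is SAP wording and one derivation. The prescribed dose is already collected. The interruption reason is also recorded, and SAP 2.6.3 already needs it to count patients interrupted for ferritin at target. The extra work is sorting interruption records by reason.

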# 3. Dose Intensity and Relative Dose Intensity

• Actual Dose Intensity (DI) for subjects with non-zero duration of exposure is defined as follows:

DI (mg/kg/day) = Actual Cumulative dose (mg/kg) / Duration of exposure to DFX FCT (day).

For subjects who did not take any drug the DI is by definition equal to zero. The denominator for DI, i.e., duration of exposure includes days of 0 doses.

• Planned Dose Intensity (PDI) is defined as follows:

PDI (mg/kg/day) = Planned Cumulative dose (mg/kg) / Duration of exposure to DFX FCT (day).

• Relative Dose Intensity (RDI) is defined as follows:

RDI = [DI (mg/kg/day) / PDI (mg/kg/day)]\*100.

The actual dose intensity and relative dose intensity will be summarized using descriptive statistics using the Safety Set. Additionally, categories of the RDI ( $\leq 75\%$ , >75% -90%, >90%-110%, >110%) will be summarized through frequency and percentage.

#### Dose Reduction/ Increases, Interruptions or Permanent Discontinuations

The number of subjects who have dose reductions, increases, permanent discontinuations or interruptions, and the reasons, will be summarized separately for each of the study treatment components in the DFX arm only.

'Dose Changed', 'Dose interrupted', and 'Dose permanently discontinued' fields from the DAR CRF pages will be used to determine the dose reductions, dose interruptions, and permanent discontinuations, respectively.

The corresponding fields 'Reason for dose change/dose interrupted' and 'Reason for permanent discontinuation' will be used to summarize the reasons.

A dose change is either 'change in prescribed dose level' or 'change in actual dose administered' where the dose is different from previous visit (increase or decrease). For the purpose of summarizing interruptions and reasons; in case multiple entries for interruption that are entered on consecutive days with different reasons will be counted as separate interruptions. However, if the reason is the same in these mentioned multiple entries on consecutive days, then it will be counted as one interruption.

**Dose Reduction:** When in the DAR CRF page, dose change field is equal to 'yes' and the reason for dose change is present, then a dose reduction is considered if the non-zero actual daily dose administered (mg), after weight adjustment in mg/kg, is *lower* (>15%) than the previous non-zero actual daily dose administered (mg), and after weight adjustment in mg/kg (threshold of >15% is applied to the dose adjusted for weight in mg/kg, see below, received by the subject or if the non-zero actual daily dose administered (after weight adjustment in mg/kg) is *lower* (>15%) than the dose amount based on the prescribed dose (mg/kg).

**Dose Increases:** When in the DAR CRF page, dose change field is equal to 'yes' and the reason for dose change is present, then a dose increase is considered if the non-zero actual daily dose administered (mg), after weight adjustment in mg/kg, is *higher* (>15%) than the previous non-zero actual daily dose administered (mg), and after weight adjustment in mg/kg (threshold of >15% is applied to the dose adjusted for weight in mg/kg, see below, received by the subject or if the non-zero actual daily dose administered (after weight adjustment in mg/kg) is *higher* (>15%) than the dose amount based on the prescribed dose (mg/kg).

Any dose change to correct a dosing error will not be considered a dose reduction (subject goes back to previous prescribed/actual dose after a dose change due to dosing error) or a resumption of dose as per protocol after an interruption (subject goes back to previous prescribed/actual dose after a dose interruption as per protocol). The threshold of 15% is applied to the percentage change of dose calculated by ( $D_{previous}$ - $D_{current}/D_{previous}$ ) X 100.

For example, due to weight adjustments when calculating actual dose differences between current and previous dose, 15% increment or decrement is checked when comparing current non-zero actual dose with previous non-zero actual dose when checking for dose resumption after an interruption as per protocol.

Dose reductions/increases will be derived programmatically, and number of dose reductions/increases will be reported.

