6.1.1 Dosing regimen

Study treatments	Pharmaceutical form and route of administration	Dose	Frequency and/or Regimen
Deferasirox FCT	Tablet for oral use	7 mg/kg (Initial dose)	Daily
Phlebotomy	Venipuncture	NA	determined by PI

Table 6-1 Dose and treatment schedule

After a 4-week screening period, eligible patients will be randomized 2:1 to receive deferasirox FCT or phlebotomy.

Patients randomized to deferasirox FCT will receive 7 mg/kg once daily. The daily dose is calculated based on the patient's weight, then rounded up or down to the nearest whole tablet according to the available strengths of deferasirox FCT tablets (90 mg, 180 mg, and 360 mg; see Appendix 14.1). After 3 months (12 weeks), adjust dose as needed based on SF levels listed below with the maximum dose adjustment of 3.5 mg/kg/day per month.

- SF < $300 \mu g/L$ Decrease to 3.5 mg/kg/day
- SF 300-1000 µg/L Maintain 7 mg/kg/day
- SF > 1000-2000 μ g/L Increase to 10.5 mg/kg/day
- SF > 2000 μ g/L Increase to 14 mg/kg/day

When SF reaches the study target $\leq 100 \ \mu g/L$, deferasirox FCT must be interrupted and the patient enters the maintenance phase.

During the maintenance phase, when SF \geq 300 µg/L, deferasirox FCT 3.5 mg/kg/day may be re-initiated. If deferasirox FCT 3.5 mg/kg/day is not controlling SF and it continues to increase, increase to a maximum 7 mg/kg/day. Treat until the SF reaches \leq 100 µg/L, then interrupt treatment again.

During regular study visits, the investigator or pharmacist will dispense the appropriate number of deferasirox FCT tablets to each patient. The number of tablets of each strength dispensed will be recorded in the study Drug Dosing Log. Each time deferasirox FCT is dispensed, the investigator must provide detailed instructions to patients, instruct them to take the assigned amount of study drug, and return all unused study medication every 4 weeks. Returned study medication must be counted and recorded. The field monitor must note the drug accountability during site visits and at the completion of the trial.

Medication labels must be in the local language and comply with the legal requirements of the countries where the study is implemented. Labels will have study identifier and storage conditions for the study drug, but no patient information.

Patients should swallow the required number of deferasirox FCT, with or without a light meal, and around the same time each day.

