14.1 Dosing tables (Deferasirox FCT)

For each patient the investigator and/or pharmacist will calculate a target daily dose taking into account patient's body weight. When the calculated dose cannot be reached with the deferasirox FCT strengths available, the closest daily dose available will be prescribed.

The following dosing table provides an efficient combination of tablet strengths reaching a certain daily dose for each body weight range.

These dosing tables have been constructed for each dosing group using lower and upper body weight limits of 35 and 140 kg, respectively. This is taking into account that the study will enroll male or female adults.

Table 14-1	Dosing table for 3.5 mg/kg/day of Deferasirox FCT
------------	---

Pt Weight in Kg	Closest Dose	90 mg	180 mg	360 mg
35 - 38	90 mg	1	-	-
39 - 64	180 mg	-	1	-
65 - 90	270 mg	1	1	-
91 - 115	360 mg	-	-	1
116 - 140	450 mg	1	-	1

Pt Weight in Kg	Closest Dose	90 mg	180 mg	360 mg
35 - 45	270 mg	1	1	-
46 - 57	360 mg	-	-	1
58 - 70	450 mg	1	-	1
71 - 83	540 mg	-	1	1
84 - 96	630 mg	1	1	1
97 - 109	720 mg	-	-	2
110 - 122	810 mg	1	-	2
123 - 135	900 mg	-	1	2
136 - 140	990 mg	1	1	2

Table 14-2	Dosing table for 7 mg/kg/day of Deferasirox	FCT
	bosing table for a mg/kg/day of belefasitor	

	0	007		
Pt Weight in Kg	Closest Dose	90 mg	180 mg	360 mg
35 - 38	360 mg	-	-	1
39 - 47	450 mg	1	-	1
48 - 55	540 mg	-	1	1
56 - 64	630 mg	1	1	1
65 - 72	720 mg	-	-	2
73 - 81	810 mg	1	-	2
82 - 90	900 mg	-	1	2
91 - 98	990 mg	1	1	2
99 - 107	1080 mg	-	-	3
108 - 115	1170 mg	1	-	3
116 - 124	1260 mg	-	1	3
125 - 132	1350 mg	1	1	3
133 - 140	1440 mg	-	-	4

Table 14-3	Dosing table f	or 10.5 mg/kg/day	of Deferasirox FCT
------------	----------------	-------------------	--------------------

Table 14-4		-4	14	е	bl	Та	
------------	--	----	----	---	----	----	--

Novartis

Amended Protocol Version 01 (Clean)

Dosing table for 14 mg/kg/day of Deferasirox FCT

Pt Weight in Kg	Closest Dose	90 mg	180 mg	360 mg
35	450 mg	1	-	1
36 - 41	540 mg	-	1	1
42 - 48	630 mg	1	1	1
49 - 54	720 mg	-	-	2
55 - 61	810 mg	1	-	2
62 - 67	900 mg	-	1	2
68 - 73	990 mg	1	1	2
74 - 80	1080 mg	-	-	3
81 - 86	1170 mg	1	-	3
87 - 93	1260 mg	-	1	3
94 - 99	1350 mg	1	1	3
100 - 106	1440 mg	-	-	4
107 - 112	1530 mg	1	-	4
113 - 118	1620 mg	-	1	4
119 - 125	1710 mg	1	1	4
126 - 131	1800 mg	-	-	5
132 - 138	1890 mg	1	-	5
139 - 140	1980 mg	-	1	5

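### At body weights of 39–44 and 65–67 kg, the SAP's 15% rule counts a correct step-down from 7 to 3.5 mg/kg/day as both a dose reduction and a dose increase

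*SAP*

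**What the plan says.** SAP 2.3.1 (Dose Reduction/ Increases, Interruptions or Permanent Discontinuations) applies its definitions only when the "dose change field is equal to 'yes' and the reason for dose change is present". A reduction or an increase is then declared by either of two comparisons, joined by *or*:

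1. the actual mg/kg dose is more than 15% lower (or higher) than the previous non-zero actual dose;
2. the actual mg/kg dose is more than 15% lower (or higher) "than the dose amount based on the prescribed dose (mg/kg").

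The SAP also writes that "The threshold of 15% is applied to the percentage change of dose calculated by" the difference between previous and current dose over the previous dose. It gives no formula for the second comparison and does not say which comparison prevails.

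The prescribed dose is "collected on the CRF page as dose prescribed in mg/kg/day" (SAP 2.3.1, Cumulative Dose), and the section on daily dose confirms the unit: "The planned dose in the eCRF is reported in mg/Kg unit". The actual dose is obtained by "dividing the total daily dose collected on the CRF page in mg by the current weight (kg").

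Protocol 6.1.1 has the calculated dose "rounded up or down to the nearest whole tablet according to the available strengths" of 90, 180 and 360 mg. Appendix 14.1 adds: "When the calculated dose cannot be reached with the deferasirox FCT strengths available, the closest daily dose available will be prescribed".

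**The concern.** The second comparison sets a tablet-rounded dose against an unrounded one. Tablets come in steps of 90 mg, so rounding can move the dose by up to 45 mg. At 3.5 mg/kg/day, 45 mg exceeds 15% of the target for any weight below 45 / (0.15 × 3.5) = 85.7 kg, so rounding alone can cross the threshold at ordinary adult weights.

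The 3.5 mg/kg/day level has a defined place in the protocol. It is the dose after week 12 when serum ferritin is below 300 µg/L, and the dose at re-initiation after an interruption for reaching target. A move to it is a recorded change with a reason, so it meets the SAP's entry condition. Read literally, the rule would put some dose cuts made exactly as the protocol directs into the dose-increase row, together with their reasons.

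**Working it through.** **Inputs.** Tablet doses by weight from Protocol Tables 14-1 to 14-4 (35 to 140 kg, 106 whole-kg weights); the 15% threshold and the two comparisons from SAP 2.3.1.

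**Step 1. Reproduce the tables.** The nearest multiple of 90 mg to (dose level × weight) returns every entry in all four tables. The tables are correct.

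**Step 2. Deviation of the table dose from the nominal dose.** Deviation = (table mg / weight) / level − 1.

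| Level (mg/kg/day) | Lowest | Highest | Weights beyond ±15% |
|---|---|---|---|
| 3.5 | −32.3% (38 kg) | +31.9% (39 kg) | 17 of 106 |
| 7 | −14.3% (45 kg) | +11.8% (46 kg) | 0 |
| 10.5 | −9.8% (38 kg) | +9.9% (39 kg) | 0 |
| 14 | −8.2% (35 kg) | +7.1% (36 kg) | 0 |

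The 17 weights at 3.5 mg/kg/day divide into:

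- more than 15% above nominal: 39–44 and 65–67 kg (9 weights);
- more than 15% below nominal: 35–38 and 61–64 kg (8 weights).

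Values at the edges of the bands:

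| Weight (kg) | Table dose (mg) | mg/kg | Deviation from 3.5 |
|---|---|---|---|
| 44 | 180 | 4.09 | +16.9% |
| 45 | 180 | 4.00 | +14.3% |
| 60 | 180 | 3.00 | −14.3% |
| 61 | 180 | 2.95 | −15.7% |
| 64 | 180 | 2.81 | −19.6% |
| 65 | 270 | 4.15 | +18.7% |
| 67 | 270 | 4.03 | +15.1% |
| 68 | 270 | 3.97 | +13.4% |

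**Step 3. Apply both comparisons to a correct step from 7 to 3.5 mg/kg/day at constant weight.**

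- *Against the previous dose:* the fall is at least 33.3% at every weight, so all 106 weights give a reduction.
- *Against the prescribed dose:* the nine high weights also give an increase.

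At 65 kg: 270/450 − 1 = −40.0% (reduction), and (270/65)/3.5 − 1 = 4.154/3.5 − 1 = +18.7% (increase). At 39–44 kg: 180/270 − 1 = −33.3%, with +31.9% down to +16.9% against 3.5.

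At the eight low weights the second comparison also says reduction, which the first has already established. No false count is added on this step.

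A step from 10.5 to 3.5 mg/kg/day double-counts at the same nine weights.

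**Step 4. Sensitivity to the missing formula.** If the second comparison is divided by the actual dose instead of the prescribed dose, the high bands become 39–43 and 65 kg. The problem shrinks but remains.

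**Step 5. How many patients.** The documents give no weight distribution. Assume Normal with SD 15 kg and weights rounded to whole kg, so the bands are 38.5–44.5 and 64.5–67.5 kg:

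| Assumed mean (kg) | 39–44 kg | 65–67 kg | Total |
|---|---|---|---|
| 85 | 0.2% | 3.6% | 3.8% |
| 80 | 0.6% | 5.2% | 5.8% |
| 70 | 2.7% | 7.7% | 10.4% |

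These are shares of patients by weight alone. Only those who move to 3.5 mg/kg/day can be miscounted, and the documents do not give that proportion.

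**The case against.** The strongest reply is that the SAP refers to a dose amount *based on* the prescribed dose, not to the prescribed dose itself. Since Appendix 14.1 says the closest available dose is what gets prescribed, the reference could be the table's tablet amount. The deviation would then be zero at every weight. The wording permits this, but the SAP never says it. It compares in mg/kg and records the prescribed dose as a mg/kg figure. Because the counts are derived programmatically, a programmer would have to choose, and the nominal reading is the more natural one.

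A second reply is that SAP 2.3.1 already makes exceptions. It does, but only for correcting a dosing error and for returning to the previous dose after a per-protocol interruption. A patient interrupted at 7 and restarted at 3.5 mg/kg/day does not return to the previous dose, so neither exception applies.

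A third reply is that the consequence is small and visible: the subject-level dose listings with reasons would expose these cases. That stands.

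Some stronger readings are tempting and do not hold:

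- *A reader might infer that ordinary rounding at 3.5 mg/kg/day is itself counted as a dose change.* It is not. A patient who stays on that dose has no change recorded and is not counted.
- *A reader might take all 17 weights, about 11% of patients under Normal(80, 15), as miscounted.* Eight of those weights add no false count on the step-down from 7 mg/kg/day.
- *A reader might infer that the step-down is recorded as an increase instead of a reduction.* It is recorded as both; the true reduction is not lost.

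**Conclusion.** The point holds in a narrow form. Followed as written, the SAP counts a correct step-down from 7 to 3.5 mg/kg/day as both a reduction and an increase at nine whole-kg weights (39–44 and 65–67 kg). For most adults the relevant band is probably the three weights 65–67 kg. This rests on reading the reference amount as the nominal mg/kg value, which the SAP's other definitions favour but do not settle.

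Under the assumed weight distributions, roughly 4% to 10% of patients lie in the bands, and only those among them who reach 3.5 mg/kg/day are affected. The dose-increase count in the deferasirox arm would be somewhat too high. The response rate, the ocular adverse event analysis and the dosing tables are unaffected. It is a minor point, worth correcting because the correction is cheap.

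**What to change.** Two changes to SAP 2.3.1:

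1. In the second comparison, define the reference amount as the tablet dose in mg from Protocol Tables 14-1 to 14-4 for the prescribed level and the patient's current weight, and write out the formula with that amount as denominator. Dosing-table rounding then gives zero deviation at all 106 weights. The weight should be the one from which the new dose was set. Protocol Table 6-2 does not require recalculation for weight changes under 10%, and a drift from 65 to 64 kg would move the table dose from 270 to 180 mg, a spurious 270/180 − 1 = +50%.
2. State that the comparison with the previous dose takes precedence, so that one change cannot be counted as both a reduction and an increase.

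Deleting the second comparison would also remove the false increases on this step-down, but it would lose the means of detecting actual dosing that departs from the prescription.

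The cost is a few lines of SAP wording and one derivation. No dosing rule and no data collection changes.
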